#### Data Monitoring Committee

An independent DMC will review safety and efficacy data and will make recommendations whether to continue or terminate the study. The DMC analyses and operations will be formally separated from the sponsor, the investigators, and the SC. Details on the composition of the committee, its procedures and interactions are provided in a separate DMC Charter.

#### Clinical Event Committee

The study is set up with prospective centralized blinded adjudication of all cardio/cerebrovascular trigger events. The prospectively defined adjudication process will assess cardiac and neurological vascular events through an independent, blinded, external Clinical Event Committee (CEC). Details on the composition of the committee, its procedures and interactions are provided in a separate CEC charter.

Additionally, separate independent, blinded, external committees will be set up for adjudication of renal events and pancreatic events. The adjudication process for renal events and pancreatic events will be clarified in a separate **the** CEC charter.

### **3.2 DISCUSSION OF TRIAL DESIGN, INCLUDING THE CHOICE OF CONTROL GROUP(S)**

A wide variety of antidiabetic medications are available for the treatment of T2DM, but it is unclear how these drugs compare with respect to long term CV risk and microvascular outcomes [\[R11-4860\]](#). The aim of this study is to have patients with T2DM on various antidiabetic background therapies represented to evaluate the long term CV and microvascular safety of linagliptin in a real life clinical setting.

The placebo-controlled design is considered ethically acceptable on the basis of appropriate criteria for patient discontinuation, ability to change background treatment to maintain, or obtain, sufficient level of glycaemic control as defined in relevant local and regional guidelines for optimized standard of care.

The treatment period is planned until the necessary number of by adjudication confirmed primary endpoint events is observed, to demonstrate non-inferiority of linagliptin compared to placebo when added on to standard of care.

Treatment with linagliptin will be compared against placebo. The treatment goal for HbA1c in this trial, according to most international guidelines, will be a target of  $\leq 7.0\%$ , using open-label titration and addition of non-study therapies in both arms to achieve this goal throughout the trial. During the trial, additional therapy will be allowed, and encouraged, if HbA1c  $> 7.5\%$  during the trial treatment phase in accordance with guidelines. This is considered important to ensure that an optimal level of standard of care is reached in both arms of the trial. However, the decision to titrate or initiate medication to optimize glycaemic control will remain with the investigator and the patients' health care providers in accordance with appropriate local treatment guidelines.

**Proprietary confidential information.**

© 2016 Boehringer Ingelheim International GmbH or one or more of its affiliated companies. All rights reserved.

This document may not - in full or in part - be passed on, reproduced, published or otherwise used without prior written permission.

The protocol also encourages the investigators and the patients' health care providers to treat all other CV risk factors (e.g. lipid levels, blood pressure, albuminuria, unhealthy lifestyle, smoking) according to an optimal level of local/regional standard of care. In a high CV risk population with renal impairment (i.e., albuminuria or eGFR [modification of diet in renal disease (MDRD) formula] 15-75 mL/min/1.73 m^2), this usually implies liberal use (if tolerated or not contraindicated) of statins, beta-blockers, calcium channel blockers, platelet inhibitors etc. This should be conducted in the context of local or regional guidance for primary or secondary CV risk prevention.

As in management of any patient with diabetic nephropathy and hypertension, the investigator may consider referral to a physician experienced in the care of kidney disease and hypertension for uncertainty about treatment. In particular it is expected that the patients at least are treated with either an angiotensin converting enzyme inhibitor (ACEi) or angiotensin receptor blocker (ARB) therapy (if one class is not tolerated, the other should be substituted) and that the target blood pressure (BP) goal is < 130/80 mmHg. When ACE inhibitors, ARBs, or diuretics are used, additional monitoring apart from the 24 week assessments in the protocol of serum creatinine, is at the investigators discretion.

The background medication will not be provided as part of the clinical trial supplies, unless required by local laws and regulations. The investigator can adjust the antihypertensive therapy, or other needed therapy, according to local and international recommendations, if better BP control is warranted during the course of the trial.

### 3.3 SELECTION OF TRIAL POPULATION

An appropriate number of patients will be screened (synonym enrolled) for the trial in approximately 600 study centres in up to 35 countries to ensure that an estimated 8300 **7000** patients are randomized (4150 **3500** to each treatment group) and evaluable. Investigators who fail to randomize at least one study subject in the first 12 weeks of the trial may be excluded from further participation. If enrolment is delayed, additional centres may be initiated.

Screening of patients for this trial is competitive, i.e. screening for the trial will stop at all centres when a sufficient number of patients have been randomized to trial treatment. Investigators will be notified when screening is complete and will not be allowed to recruit additional patients thereafter. Patients who have completed visit 1 procedures prior to notification of the termination of recruitment will be allowed to be randomized in the study, if they meet all eligibility criteria. Subject eligibility will be based upon a complete medical history including a physical examination and clinical laboratory tests. Judgement of the clinical relevance of a concomitant disease is at the discretion of the investigator.

Re-screening and/or re-testing (of assessments) is permitted once.

A log of all patients included into the study (i.e. having given informed consent) will be maintained in the investigator site file (ISF) at the investigational site irrespective of whether they have been treated with investigational drug or not.

Proprietary confidential information.

© 2016 Boehringer Ingelheim International GmbH or one or more of its affiliated companies. All rights reserved.

This document may not - in full or in part - be passed on, reproduced, published or otherwise used without prior written permission.

### 3.3.1 Main diagnosis for study entry

Patients with documented diagnosis of T2DM at high risk of CV events and meeting all other eligibility criteria can be enrolled in the study.

### 3.3.2 Inclusion criteria

- 1) Documented diagnosis of T2DM before visit 1 (screening).
- 2) Male or female patients who are drug-naïve or pre-treated with any antidiabetic background therapy, excluding treatment with GLP-1 receptor agonists, DPP-4 inhibitors or SGLT-2 inhibitors if  $\geq 7$  consecutive days.
- 3) Stable antidiabetic background medication (unchanged daily dose) for at least 8 weeks prior to randomization. If insulin is part of the background therapy, the average daily insulin dose should not have been changed by more than 10% within the 8 weeks prior to randomization compared with the daily insulin dose at randomization.
- 4) HbA1c of  $\geq 6.5\%$  and  $\leq 10.0\%$  at visit 1 (screening).
- 5) Age  $\geq 18$  years at visit 1 (screening). *For Japan only: Age  $\geq 20$  years at Visit 1.*
- 6) Body Mass Index (BMI)  $\leq 45 \text{ kg/m}^2$  at visit 1 (screening).
- 7) Signed and dated written informed consent by date of visit 1 (screening) in accordance with GCP and local legislation prior to any study related procedure.
- 8) High risk of CV events (**I and/or II**):

I.	
Albuminuria (UACR <math>\geq 30 \text{ mg/g}</math> creatinine or <math>\geq 30 \mu\text{g/min}</math> [microgram albumin per minute] or <math>\geq 30 \text{ mg/24 h}</math> [milligram albumin per 24 hours] in two out of three unrelated spot urine or timed samples in the last 24 months prior to randomization)* AND previous macrovascular disease, defined as either one or more:

a	Confirmed history of MI ( $> 2$ months prior to Visit 1)
b	
Advanced coronary artery disease, defined by any one of the following:
 

• <math>\geq 50\%</math> narrowing of the luminal diameter in 2 or more major coronary arteries by coronary angiography, MRI angiography or CT angiography;

 
Definition of major coronary arteries: LAD (Left Anterior Descending). CX (Circumflex) or RCA (right coronary artery)
 

• Left main stem coronary artery with <math>\geq 50\%</math> narrowing of the luminal diameter by coronary angiography, MRI angiography or CT angiography;

• Prior percutaneous or surgical revascularization of <math>\geq 2</math> major coronary arteries at least 2 months prior to Visit 1 (screening);

• The combination of prior percutaneous or surgical revascularization of 1 major coronary artery at least 2 months prior to visit 1 (screening), and <math>\geq 50\%</math> narrowing of the luminal diameter by coronary angiography, MRI angiography or CT angiography of at least 1 additional major coronary artery.

Proprietary confidential information.

© 2016 Boehringer Ingelheim International GmbH or one or more of its affiliated companies. All rights reserved.

This document may not - in full or in part - be passed on, reproduced, published or otherwise used without prior written permission.

	c	
High-risk single-vessel coronary artery disease, defined as the presence of <math>\geq 50\%</math> narrowing of the luminal diameter of one major coronary artery by coronary angiography, MRI angiography or CT angiography in patients not revascularised:
 
AND at least one of the following:
 

• A positive non invasive stress test, confirmed by either:

○ a positive ECG exercise tolerance test in patients without left bundle branch block, Wolff-Parkinson-White syndrome, left ventricular hypertrophy with repolarization abnormality, or paced ventricular rhythm, atrial fibrillation in case of abnormal ST-T segments;

○ a positive stress echocardiogram showing induced regional systolic wall motion abnormalities;

○ a positive nuclear myocardial perfusion imaging stress test showing stress-induced reversible perfusion abnormality;

○ a positive cardiac stress perfusion MRI showing a stress induced perfusion defect;

• Patient discharged from hospital with a documented diagnosis of unstable angina pectoris between 2 and 12 months prior to visit 1 (screening).

	d	History of ischemic or haemorrhagic stroke ( $>3$ months prior to visit 1)
	e	Presence of carotid artery disease (symptomatic or not) documented by either: 

○ imaging techniques with at least one lesion estimated to be <math>\geq 50\%</math> narrowing of the luminal diameter;

○ prior percutaneous or surgical carotid revascularization.

	f	Presence of peripheral artery disease documented by either: 

○ previous limb angioplasty, stenting or bypass surgery;

○ previous limb or foot amputation due to macrocirculatory insufficiency;

○ angiographic evidence of peripheral artery stenosis <math>\geq 50\%</math> narrowing of the luminal diameter in at least one limb (definition of peripheral artery: common iliac artery, internal iliac artery, external iliac artery, femoral artery, popliteal artery).

II.		
Evidence of impaired renal function with predefined UACR, with or without CV comorbidities, defined as follows (and/or criteria):
 

• Impaired renal function (as defined by MDRD formula) with an eGFR: <math>15- < 45</math> mL/min/<math>1.73\text{ m}^2</math> at visit 1 (screening) with any UACR.

• Impaired renal function (as defined by MDRD formula) with an eGFR <math>\geq 45-75</math> mL/min/<math>1.73\text{ m}^2</math> at visit 1 (screening) with an UACR <math>> 200</math> mg/g creatinine or <math>> 200</math> <math>\mu\text{g}/\text{min}</math> (microgram albumin per minute) or <math>> 200</math> mg/24 h [milligram albumin per 24 hours] demonstrated in two out of three unrelated spot urine or timed samples in the last 24 months prior to randomization*.

\*If the UACR result at Visit 2 is required to fulfil inclusion criterion 8, randomization may be postponed until the laboratory results are known.

Note: To ensure appropriate representation of patients from the different CV risk categories, the trial team will monitor the proportion of patients being recruited into these categories (trial level, and by region and/or country if appropriate). In consultation with the SC, limitation of recruitment of a particular category may be arranged (trial level, or per region and/or country level). This process will be implemented to ensure a proper distribution of CV risk categories worldwide.

### 3.3.3 Exclusion criteria

- 1) Type 1 diabetes mellitus.
- 2) Treatment ( $\geq 7$  consecutive days) with GLP-1 receptor agonists, other DPP-4 inhibitors or SGLT-2 inhibitors prior to informed consent. Note: This also includes clinical trials where these antidiabetic drugs have been provided to the patient.
- 3) Active liver disease or impaired hepatic function, defined by serum levels of either ALT (SGPT), AST (SGOT), or alkaline phosphatase (AP)  $\geq 3 \times$  upper limit of normal (ULN) as determined at Visit 1.
- 4) eGFR  $< 15 \text{ ml/min}/\text{1.73 m}^2$  (severe renal impairment or ESRD, MDRD formula), as determined during screening at Visit 1 and/or the need for maintenance dialysis.
- 5) Any previous (or planned within next 12 months) bariatric surgery (open or laparoscopic) or intervention (gastric sleeve).
- 6) Pre-planned coronary artery re-vascularisation (PCI, CABG) or any previous PCI and/or CABG  $\leq 2$  months prior informed consent
- 7) Known hypersensitivity or allergy to the investigational products or its excipients.
- 8) Any previous or current alcohol or drug abuse that would interfere with trial participation in the opinion of the investigator.
- 9) Participation in another trial with an investigational drug ongoing or within 2 months prior to visit 1 (screening)\*.
- 10) Pre-menopausal women (last menstruation  $\leq 1$  year prior to informed consent) who:
  - are nursing or pregnant,
  - or are of child-bearing potential and are not practicing an acceptable method of birth control (acceptable methods of birth control include tubal ligation, transdermal patch, intra uterine devices/systems (IUDs/IUSs), oral, implantable or injectable contraceptives, sexual abstinence (if allowed by local authorities), double barrier method and vasectomised partner) or do not plan to continue using acceptable method of birth control throughout the study and do not agree to submit to periodic pregnancy testing during participation in the trial.
- 11) Patients considered unreliable by the investigator concerning the requirements for follow-up during the study and/or compliance with study drug administration, have a life expectancy less than 5 years for non-CV causes, or have cancer other than non-melanoma

Proprietary confidential information.

© 2016 Boehringer Ingelheim International GmbH or one or more of its affiliated companies. All rights reserved.

This document may not - in full or in part - be passed on, reproduced, published or otherwise used without prior written permission.

skin cancer within last 3 years, or has any other condition than mentioned which in the opinion of the investigator, would not allow safe participation in the study.

- 12) Acute coronary syndrome (ACS), diagnosed  $\leq$  2 months prior to visit 1 (screening).
- 13) Stroke or TIA  $\leq$  3 months prior to visit 1 (screening).

### 3.3.4 Removal of patients from therapy or assessments

#### 3.3.4.1 Removal of individual patients

This is a long-term safety **outcome** study **and every effort should be made by the site staff to encourage patients to remain in the study and on study drug if medically safe.**

Patients who discontinue study drug prematurely should be observed until study end **as if they were still receiving blinded study treatment**. Patients who prematurely discontinue study drug **should** remain in the study. Study assessments may be omitted if a patient is willing to return to the pre-defined study visits, with exception of **adverse events, outcome events, concomitant therapy and laboratory testing of creatinine for the calculation of the eGFR.**

If a patient who prematurely discontinued study drug is not willing to return at the pre-defined regular visit schedule, at minimum a yearly telephone call (preferably every 6 months) and a telephone call at study end will be **asked for required**, to document the occurrence of outcome events and vital status. If possible, also other AE's and concomitant therapy changes since last visit **might should** be recorded. Every attempt will be made by the investigator to ensure patients continue participating in the study during study drug interruptions and after discontinuation of study drug.

Patients who prematurely discontinue study medication **during the treatment phase** are allowed to restart the study medication at any time if appropriate in the opinion of the investigator and if not contraindicated. In this study, patients are allowed to have multiple study drug interruptions. There is no limit on either the number of study drug interruptions or the maximum length of any study drug interruption. **Investigators should routinely consider re-starting study drug at every visit following study drug discontinuation.**

**A patient should be instructed to stop the study drug only after discussion between sponsor representative and investigator, if eligibility criteria are being violated, or if the patient fails to comply with the protocol (e.g. non-attendance at study assessments).**

**Early discontinuation of study medication is not a criterion for withdrawal of consent for participating in the study.**

If a patient becomes pregnant during the trial, the study treatment will be stopped, the patient will be followed up during the study and until birth or termination of the pregnancy (see further details in [Section 5.2.2.2](#)).

If pancreatitis is suspected, the study treatment should be stopped.

**An individual patient is to be withdrawn from the study and follow up assessments only if the patient actively withdraws consent, without the need to justify the decision.**

Proprietary confidential information.

© 2016 Boehringer Ingelheim International GmbH or one or more of its affiliated companies. All rights reserved.

This document may not - in full or in part - be passed on, reproduced, published or otherwise used without prior written permission.

A patient has the right to withdraw informed consent for participation at any time for any reason. However, withdrawal of consent from study participation should be very rare and unusual. Because of this, the investigator should be involved in the discussions with the patient regarding a withdrawal of consent. Additionally, the investigator should discuss the withdrawal of consent with the sponsor representative prior to stopping study participation.

Patients that are not actively taking study drug may be less motivated to adhere to the study visit schedule. Investigators and site staff should work to detect early signs of losing interest and readily present such patients (not actively taking study drug) with the following options to encourage continued participation:

- Option 1 Continue to attend regularly scheduled study visits at the site until the study ends
- Option 2 Conduct all remaining study visits over the phone
- Option 3 Discontinue participation in remaining study activities but permit collection of vital status and CV outcome events at minimum at the end of the study through the patient or alternative person designated by the patient (e.g., family, spouse, partner, legal representative, or physician) even if only by telephone
- Option 4 Discontinue participation in remaining study activities but permit collection of vital status at minimum at the end of the trial through the patient, alternative person designated by the patient, or through review of patient's medical information from alternative sources (e.g., doctor's notes, hospital records, etc.)

Patients will be asked to choose the most rigorous form of follow-up that they are willing to comply with.

Patients who refuse all four of the above are considered to have fully withdrawn informed consent to participate in the study. A patient should be withdrawn from the study and all follow up assessments only if the patient refused all four options and withdraws informed consent, without the need to justify the decision. Where allowed, patients should be followed-up for vital status.

If the patient withdraws informed consent for participation in the study, the study will end for that patient. The patient should stop taking study medication and should be asked to complete the EOT and follow-up procedures as described in the [Flow Chart](#). Completing these procedures is strongly recommended for the patient's safety. A patient could be instructed to stop the study treatment only after discussion between sponsor representative and investigator, if eligibility criteria are being violated, or if the patient fails to comply with the protocol (e.g. non-attendance at study assessments). Patients that withdraw informed consent or discontinue from the study after randomization will not be replaced.

If a patient is lost, every effort should be made by the Investigator and site staff to contact and locate the patient before the patient is declared lost to follow-up. Investigators and site staff should use every possible allowable means to locate patients

Proprietary confidential information.

© 2016 Boehringer Ingelheim International GmbH or one or more of its affiliated companies. All rights reserved.

This document may not - in full or in part - be passed on, reproduced, published or otherwise used without prior written permission.

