### 5.2.1.1 Reporting waiver for cardiovascular-outcome events

In accordance with ICH-guideline E2A and in order to maintain the integrity of this study, CV outcome events that occur after randomization and represent an SAE are exempted from expedited reporting to health authorities. The medication code will not be broken for the purpose of expedited reporting to regulatory authorities.

CV outcome events are defined as the following components of the primary, **key** secondary and other CV endpoints:

- CV death
- non fatal MI
- silent MI
- non fatal stroke (ischemic/hemorrhagic/etiology unknown)
- hospitalisation for unstable angina pectoris
- hospitalisation ~~due to congestive~~ **for** heart failure (CHF)
- transient ischemic attack (TIA)
- coronary revascularisation procedures (PCI and CABG)
- peripheral revascularization procedures

For definitions of the CV outcome events see [Appendix 10.2](#).

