**Early discontinuation of study medication is not a criterion for withdrawal of consent for participating in the study.**

### 6.2.3 End of treatment and follow-up period

**Patients who discontinue study drug should continue study visits until study end. Study assessments may be omitted if a patient is willing to return to the pre-defined study visits, with exception , collection of adverse events, outcome events, concomitant therapy and laboratory testing of creatinine for the calculation of the eGFR.**

**If a patient who discontinued study drug is not willing to return to the pre-defined study visits, at minimum a yearly telephone call (preferably every 6 months) and a telephone call at study end will be required, to document the occurrence of outcome events and vital status. If possible, other AE's and concomitant therapy changes since last visit should be recorded. Every attempt will be made by the investigator to ensure patients continue participating in the study during study drug interruptions and after discontinuation of study drug.**

**Patients that are not actively taking study drug may be less motivated to adhere to the study visit schedule. Investigators and site staff should work to detect early signs of losing interest and readily present such patients (not actively taking study drug) with options to encourage continued participation. Refer to [section 3.3.4.1](#) for options to encourage continued participation and for details regarding patients who are lost-to-follow-up or who have withdrawn informed consent.**

~~If the patient withdraws informed consent for study participation, the study participation of the patient will end. The patient should stop taking study medication and should be asked to complete the EOT and follow up visit activities as described in the [Flow Chart](#). Completing these procedures is strongly recommended for the patient's safety.~~

Proprietary confidential information.

© 2016 Boehringer Ingelheim International GmbH or one or more of its affiliated companies. All rights reserved.

This document may not - in full or in part - be passed on, reproduced, published or otherwise used without prior written permission.

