### 7.3 PLANNED ANALYSES

The primary analyses (including all confirmatory tests described in [Section 7.2](#)) will be performed on the ~~full analysis set (FAS)~~ **Treated Set (TS)**. The ~~FAS~~ **TS** will consist of all ~~randomized~~ patients who were treated with at least one dose of study drug.

For the primary and key secondary endpoints a ‘classical intention to treat (ITT) analysis on the ~~FAS~~ **TS**’ will be done. That means that:

- the analysis set consists of the ~~FAS~~ **TS**,
- the allocated study treatment at randomization will be used for the analysis (‘as randomized’),
- all events which occur until study end will be taken into account.

A per protocol set (PPS) of patients following the trial protocol in essential criteria will be created for sensitivity analyses. Patients included in the ~~FAS~~ **TS** who have important protocol violations will be excluded from the PPS. A protocol violation (PV) will be considered important if it can be expected to have a distorting influence on the assessment of the primary endpoint.

Important protocol violations include:

- Randomized study drug: incorrect study drug taken.
- Severe violation of treatment compliance (defined as compliance with study treatment < 80% for more than 50% of the time between randomization and first endpoint (CV death, non-fatal MI, non-fatal stroke, ~~hospitalisation for unstable angina pectoris~~).
- Non-adherence to other specifications of the protocol that could bias the primary composite endpoint (e.g. limited life expectancy (< 5 years) at randomization due to various medical conditions)

Additionally a ‘30-day treatment’ **on-treatment** set (**OS**) of patients will be created for sensitivity analysis. The ‘30-day treatment’ **OS** set will include all patients with minimum treatment duration of 30-days.

All patients treated with at least one dose of study drug (the Treated Set) will be included in the safety evaluation. ~~In case only randomized patients take study drug, this set is identical to the FAS;~~ the safety analyses will be displayed ‘as randomized’.

Proprietary confidential information.

© 2016 Boehringer Ingelheim International GmbH or one or more of its affiliated companies. All rights reserved.

This document may not - in full or in part - be passed on, reproduced, published or otherwise used without prior written permission.

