## 7.4 HANDLING OF MISSING DATA

Patients with temporary or permanent study treatment termination will be followed up for CV events. Details on how to handle missing data will be outlined in detail in the trial statistical analysis plan (TSAP).

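### Collection of ESRD and eGFR events is not assured for patients who stop attending, although the renal endpoint is to be analysed as ITT with all events to study end

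*Protocol*

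**What the plan says.** Protocol 7.3 sets the analysis rule for the primary and key secondary endpoints: Treated Set, as randomized, and "all events which occur until study end will be taken into account". Protocol 3.1 adds that the ITT analysis needs every patient followed to study end, on drug or not. The key secondary endpoint (Protocol 5.1.1, SAP 5.2.1) is the first of renal death, sustained ESRD or a sustained eGFR fall of at least 40%. Under Protocol 7.2 and SAP 7.4.1 its superiority test starts at 0.8 of alpha.

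Collection for patients who stop study drug is described in several places:

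- Those still willing to attend keep adverse events, outcome events, concomitant therapy and the creatinine sample (3.3.4.1).
- Those who will not attend have a call at least yearly and at study end "to document the occurrence of outcome events and vital status" (3.3.4.1; also flow chart footnote C, 3.1 and 6.2.3). Beyond that, "If possible, other AE's and concomitant therapy changes since last visit should be recorded" (6.2.3).
- Patients losing interest are offered four options. Option 2 is "Conduct all remaining study visits over the phone". Option 3 asks them to "permit collection of vital status and CV outcome events at minimum at the end of the study". Option 4 asks them to "permit collection of vital status at minimum at the end of the trial".
- Section 7.4 states: "Patients with temporary or permanent study treatment termination will be followed up for CV events".

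The nearest definition is in 5.2.1.1, where "CV outcome events are defined as the following components of the primary", key secondary and other CV endpoints. The list that follows has no renal item.

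**The concern.** The analysis rule treats the CV and renal endpoints alike; the fallback collection rules do not. Followed to the letter, Option 3 lets a site complete its last contact without asking whether the patient has started dialysis.

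Patients who leave study visits may well include some with worsening kidney disease, so any such loss could be informative. It would fall on an endpoint with a confirmatory test and the larger initial share of alpha. At stake are some renal events and hence power, a distorted hazard ratio if the loss differs between arms, and a renal ITT analysis that in part describes only those who kept attending.

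The sponsor has already accepted the principle. Amendment 1 kept creatinine for patients off drug and cited the ITT principle, but only for those willing to return.

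**Working it through.** **1. Where each component can be found, by type of follow-up**

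| Follow-up | Renal death | ESRD (dialysis, transplantation) | eGFR fall ≥ 40% |
|---|---|---|---|
| Off drug, attending | yes | yes | yes, creatinine kept |
| Option 2 or minimum calls | through vital status | possible, but *outcome events* is undefined | no sample |
| Option 3 | through vital status | not asked for | no sample |
| Option 4 | through vital status | not asked for; patient agreed to vital status only | no sample |

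Renal death is partly protected: vital status is sought in every row, and Protocol 7.1 counts adjudicated renal death even after the censoring date. Vital status alone may not supply the cause of death. The remaining gap is ESRD under Option 3 and the creatinine component in every row below the first.

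**2. Loss to follow-up and censoring**

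SAP 6.8.4 defines loss to follow-up for 3-point MACE and for vital status; the visible text has none for the renal endpoint. Protocol 7.1 censors the renal endpoint at the last visit or a later eGFR date. SAP 7.5.1 refers the renal endpoint to 6.8.3, where the general rule allows the last telephone contact. Read literally, telephone-only time could count as renal event-free without an eGFR. SAP 6.8.3 has gaps, so a renal-specific rule may exist.

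**3. The plan's own power figures**

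Inputs from Protocol 7.6: 432 renal events at HR 0.75 (power 85%) and 210 events at HR 0.70 (power 73%), with 1:1 allocation. The one-sided level of 2.5% is stated for the first figure and taken to apply to the second. With d events,

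power = Φ(√(d/4) × |ln HR| − z₁₋α)

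- d = 432, HR 0.75, α = 0.025: √108 × 0.2877 − 1.960 = 1.030, power 84.8% (stated 85%).
- d = 210, HR 0.70, α = 0.025: √52.5 × 0.3567 − 1.960 = 0.624, power 73.4% (stated 73%).

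The renal test reaches 2.5% only if 3-point MACE superiority is first shown at 0.2 × 2.5% = 0.5%. Its initial level is 0.8 × 2.5% = 2.0% (z = 2.054).

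**4. Illustration: equal loss in both arms, one-sided 2.0%**

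The loss rates are assumptions; the documents give none.

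| Renal events missed | 432 events, HR 0.75 | 210 events, HR 0.70 |
|---|---|---|
| 0% | 82.5% | 70.2% |
| 5% | 80.5% (410.4 events) | 67.9% (199.5 events) |
| 10% | 78.3% (388.8 events) | 65.5% (189 events) |

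**5. Illustration: unequal loss**

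Approximately, observed HR = true HR × (1 − loss on linagliptin)/(1 − loss on placebo).

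- Equal loss leaves the HR unchanged.
- 10% on linagliptin against 5% on placebo turns a true HR of 1.00 into 0.90/0.95 ≈ 0.95. With a ratio of 0.95, the one-sided error at a nominal 2.0% becomes Φ(√(d/4) × 0.0513 − 2.054): about 6.4% with 432 events and 4.6% with 210.
- The reverse pattern gives 0.95/0.90 ≈ 1.06, against linagliptin.

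Nothing in the documents indicates that loss would differ by arm.

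**The case against.** A reader might infer that all follow-up of non-attenders is confined to CV events and vital status. The documents do not support that. Option 2 continues the visits by telephone with no CV limit, and the mandatory calls record outcome events without the qualifier CV. Patients are asked to choose the most rigorous form they will accept, so Option 3 applies only after clinic and telephone visits are refused.

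Nor does 5.2.1.1 make outcome events a CV list. It defines *CV outcome events*, for the purpose of a reporting waiver. The supportable statement is that the wider term is undefined in the visible text. Section 7.4 is not worded as exclusive either, and it leaves detail to the SAP.

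Other routes exist. Worsening of pre-existing disease is recorded as an adverse event (5.2.2.1), and SAEs are reportable within 24 hours of awareness (5.2.2.2). Adverse events can trigger renal adjudication (SAP 7.8.1.7), and extra creatinine is drawn if others report a rise (flow chart footnote L). Endpoint definitions and collection principles sit in the CEC charter (Protocol 10.2), which is not available here; nor is the eCRF.

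All of this stands and narrows the point. It does not remove it: these routes depend on the site learning of the event, and Option 3, which defines the contact with patients who refuse visits, does not ask for it.

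**Conclusion.** The point holds in limited form. Option 3 and Section 7.4 name only CV events (with vital status in Option 3), and outcome events in the minimum calls is not visibly defined to include renal events. Ascertainment of ESRD and eGFR decline in non-attenders is therefore not assured, while the analysis promises all events to study end.

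No figure for lost events should be given. The documents state no rate of non-attendance, and the 2.0% loss to follow-up in 7.6 belongs to the superseded calculation with 4150 patients per group. It might also be inferred that 432 is a planned renal count from which losses can be subtracted. It is one of two power assumptions, the other being 210, and the trial stops on primary events. Biased renal results should not be inferred either, since that needs loss that differs by arm.

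On the illustrative assumptions, equal loss of 5% to 10% costs about 2 to 4 points of power with 432 events and 2 to 5 with 210. This is a modest, inexpensive improvement. Confidence is moderate because the CEC charter, the eCRF and parts of SAP 6.8.3 cannot be seen.

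**What to change.** - In Option 3, ask for vital status together with CV and renal outcome events, the latter being start of maintenance dialysis, kidney transplantation and renal death.
- Define outcome events, for all follow-up contacts, to include these renal items. One definition then serves flow chart footnote C, 3.1, 3.3.4.1 and 6.2.3. Option 2 needs no change.
- Align Section 7.4 so that it refers to CV and renal events.
- Where the patient permits, request the most recent local creatinine with its date. A single value cannot by itself show a sustained fall, so treat it as a trigger. Send it and any positive answer to renal adjudication.
- In the SAP, define loss to follow-up for the renal endpoint, report it by arm, and state which censoring date applies to telephone-only time.

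The cost is amendment wording, a few questions in contacts that already take place, and some local records to retrieve. The creatinine component will remain incomplete for patients with no available local result.
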